### **14.6. Analysis Sets**

The following analysis populations will be used to complete the analyses of data:

- **Safety Population:** The safety population will include all enrolled subjects who have the investigational device inserted, regardless if RF energy is delivered.
- **Effectiveness Population:** The effectiveness population will include all enrolled subjects who have had the investigational device inserted and underwent ablation with the study catheter used in conjunction with TGA mode for PVI. The subjects without any TGA mode application for PVI will be excluded from the effectiveness population.
- **Neurological Assessment Evaluable (NAE) Population:** The NAE Population will include all enrolled subjects who meet the eligibility criteria, have been treated with the study catheter and had any post-ablation neurological assessment. Assessment of incidence of new lesions or deficits requires availability of the associated pre-procedural assessment.

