### **14.7. Sample Size Justification**

This is a clinical feasibility study for evaluation of safety and acute performance of THERMOCOOL SMARTTOUCH® SF-5D system with TGA mode application for PVI. This clinical investigation is intended to provide preliminary estimates of workflow and acute outcomes. Enrollment in the clinical investigation will be 50 subjects, distributed over up to 10 centers in Europe. Minimum attrition is expected for safety assessment. No more than 10% attrition is expected to assess effectiveness outcomes.

Because this study is a feasibility study, there is no statistical power calculation and no hypothesis to be tested. 50 subjects are deemed sufficient to clinically characterize safety and acute outcomes.

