### **14.8.3. Demographic and Baseline Characteristics**

All demographic and baseline characteristics, procedural, and immediate post-operative details will be summarized and listed overall in the safety population.

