#### **14.8.4.3. Analyses of Secondary and Additional Endpoints**

No formal statistical hypotheses and inferential statistics will be formulated and performed for the secondary and additional endpoints. Details of analyses methods for secondary and additional endpoints will be provided in SAP.

Secondary Safety analysis for SADEs and AEs will be performed on the Safety Population. The neurological assessment related endpoints will be analyzed in the NAE population. Secondary Effectiveness (including Procedural Data) will be performed on the Effectiveness Population.

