5.2 Secondary Endpoints

- **Safety**
 - Incidence of Serious Adverse Device Effects (SADEs)
 - Incidence of Serious Adverse Events (SAEs) within 7 days (early-onset), >7-30 days (peri-procedural) and >30 days (late onset) of initial ablation procedure
 - Incidence of non-serious adverse events
 - Incidence of pre-and post-ablation asymptomatic and symptomatic cerebral emboli as determined by MRI evaluations
 - Incidence of new or worsening neurological deficits compared to baseline
 - Summary of NIHSS, mRS and MoCA scores at baseline and follow-up timepoints
- **Effectiveness**
 - PVI achieved with TGA mode only among all targeted veins and by subject
 - PVI achieved with combined use of TGA and Q-mode among all targeted veins and by subject
 - Ablation of acute reconnection (touch-up) among all targeted veins and by subject
 - Ablation by a non-study catheter among all targeted veins and by subject
 - Touch-up applications with TGA, Q-mode and non-study catheter applications
- **Additional analyses on procedural data, including but not limited to:**
 - Use of QDOT Micro™ catheter ablation outside the PV area
 - Use of a non-study catheter for ablation outside the PV area

- Total procedure time, mapping time, PV ablation time, total ablation time, RF application time, LA dwell time
- Total number of RF applications, % TGA applications and % Q-mode applications
- Anatomical location of touch-up applications
- Temperature, power, contact force, impedance
- Total Fluoroscopy time/dose

6 Levels of Significance

All data will be summarized by descriptive analyses. No formal statistical inference will be made. Sub-analyses will be done for subjects where TGA was the only application mode used and for subjects where applications were done through a combination of TGA and Q-mode. Where confidence intervals are used they will be two-sided 95% confidence intervals, unless stated otherwise.

7 Analysis Sets

The following analysis populations will be used to complete the analyses of data:

- **Safety Population (SP):** The safety population will include all enrolled subjects who have the investigational device inserted, regardless if RF energy is delivered. All safety analyses will be performed on the Safety Population.

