The number of PV isolation achieved among all targeted veins and the number and percentage of subjects with PVI achieved with TGA mode only will be summarized and listed. The number of PV isolation achieved among all targeted veins and the number and percentage of subjects with PVI achieved with combined use of TGA and Q-mode will be summarized and listed. The number of PV with acute reconnection (touch-up) among all targeted veins and the number and percentage of subjects with touch-up ablations will be summarized and listed. Touch-up applications with TGA, Q-mode and non-study catheter will be summarized by PVs and subjects. PV ablations by a non-study catheter among all targeted veins and by subject will be summarized and listed. These analyses will be performed in the effectiveness population.

Additional Analyses on Procedural Data

Procedural data will be summarized and listed. For continuous variables, number of subjects with non-missing data, mean, standard deviation, median, 25% percentile, 75% percentile, minimum, and maximum will be reported. For categorical variables, the frequency and percentage will be presented for each category. Procedural data will be summarized in the effectiveness population.

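### The protocol puts procedural data in two different populations, and the SAP uses only the one that leaves out subjects who never received TGA for PVI

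*SAP*

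**What the plan says.** Three places assign a population to procedural data, and they do not agree.

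- Protocol 14.8.3, under demographic and baseline characteristics: "All demographic and baseline characteristics, procedural, and immediate post-operative details will be summarized and listed overall in the safety population".
- Protocol 14.8.4.3, on secondary and additional endpoints: "Secondary Effectiveness (including Procedural Data) will be performed on the Effectiveness Population".
- SAP 10.4, on additional procedural analyses: "Procedural data will be summarized in the effectiveness population".

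SAP 10.3, which corresponds to Protocol 14.8.3, covers baseline items only. It does not mention procedural details, names no population and does not explain the difference.

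Protocol 14.6 defines the two sets. For the Safety Population: "The safety population will include all enrolled subjects who have the investigational device inserted, regardless if RF energy is delivered". For the Effectiveness Population the subject must have been ablated with the study catheter in TGA mode for PVI, and "The subjects without any TGA mode application for PVI will be excluded from the effectiveness population". SAP 7 applies the same rules.

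The procedural variables in SAP 5.2 include "Total procedure time, mapping time, PV ablation time, total ablation time, RF application time, LA dwell time", fluoroscopy time and dose, and "Total number of RF applications, % TGA applications and % Q-mode applications".

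**The concern.** There are two linked problems.

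First, the SAP does not deliver what Protocol 14.8.3 promises. Its only procedural summary is in the narrower set. Subjects with the catheter inserted but no RF delivered are a foreseen group: Protocol 4.4 defines them as discontinued, and they also count as evaluable, so they sit within the 50 evaluable subjects of Protocol 4.3.2. Protocol 8.2.3 has total procedure time, left atrial dwell time and fluoroscopy recorded as part of the procedure, yet these subjects' values would not enter the procedural summaries. Adverse events are counted in the Safety Population, so an event in such a subject would have no counterpart in the procedural table.

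Second, entry to the Effectiveness Population depends on TGA use, and the share of applications given in TGA mode is one of the results being summarised. Removing subjects whose TGA share is zero can only raise that share or leave it unchanged. Workflow is a stated interest of the study (Protocol 2 and 14.7), so its denominator should be unambiguous.

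**Working it through.** The plan gives no figure for this point, so there is nothing to reproduce. The steps below establish who is lost and then bound the effect.

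**Who is lost.** Protocol 8.2.2.4 makes TGA the first mode and allows Q-mode only once the investigator judges that TGA cannot achieve PVI. One TGA application for PVI keeps a subject in the Effectiveness Population. A failed TGA attempt completed in Q-mode or with another catheter is therefore retained, with its times and its low TGA share. Those lost are inserted subjects with no RF, or with RF but no TGA for PVI because of a device problem or a deviation. A subject given TGA only outside the pulmonary veins is also lost.

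**Inputs.**
- N = 50 inserted subjects (Protocol 4.3.2 and 14.7).
- k = number excluded from the Effectiveness Population, taken from 0 to 5. The upper end comes from Protocol 14.7: "No more than 10% attrition is expected to assess effectiveness outcomes", and 10% of 50 is 5. Nothing there says that this attrition consists of subjects without TGA, so k = 5 is a ceiling.
- s = mean per-subject TGA share in the Effectiveness Population. The documents give no value, so 90% and 70% are assumed. They also do not say whether the share is a mean of per-subject percentages or a pooled ratio; the mean is assumed here.

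**TGA share when all k were ablated, with 0% TGA.** Safety Population share = s × (50 − k)/50. The relative overstatement is 50/(50 − k) − 1.

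| k | Effectiveness Population size | Safety share if s = 90% | Safety share if s = 70% | Overstatement |
|---|---|---|---|---|
| 0 | 50 | 90.0% | 70.0% | 0% |
| 1 | 49 | 88.2% | 68.6% | 2.0% |
| 3 | 47 | 84.6% | 65.8% | 6.4% |
| 5 | 45 | 81.0% | 63.0% | 11.1% |

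**TGA share when some of the k had no RF.** Such subjects have no defined share and enter neither mean. If m of the k had RF in other modes only, the Safety Population share is s × (50 − k)/(50 − k + m). With k = 5, m = 2 and s = 90%, this is 45 × 90/47 = 86.2%. With m = 0 it stays at 90%.

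**Procedure time.** If the excluded subjects differ by D minutes on average, the Safety Population mean minus the Effectiveness Population mean is k × D/50. For an assumed D of 15 to 60 minutes in size:
- k = 1: 0.3 to 1.2 minutes.
- k = 5: 1.5 to 6.0 minutes.

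The sign is not known. A stopped procedure may be shorter than average, and one with a device problem may be longer.

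**The case against.** The strongest reply has four parts.

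- **The SAP governs and is consistent with itself.** Protocol 14.8.4.3 leaves the methods for secondary and additional endpoints to the SAP, and an analyst who follows SAP 10.4 gets one answer. This stands, but it does not remove the conflict within the protocol. If 14.8.3 was meant as a separate overall summary, which no document says, then the SAP omits it.
- **The Effectiveness Population is a defensible choice.** The objective concerns the system used with TGA, and describing TGA workflow in those who received it is reasonable. This also stands, and it is the reason to keep that population as a second column.
- **The exclusions would be partly visible.** Disposition is tabulated for all enrolled subjects (SAP 10.2). SAP 10.4 also promises procedural listings, and only its summaries are tied explicitly to the Effectiveness Population. The gap in counts could be seen, but not its effect on the summaries. The mode subgroups in SAP 10.7 have no category for subjects without TGA.
- **The effect is small and descriptive.** This stands.

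A reader might infer that the hardest procedures are being removed and that times are therefore understated. The documents do not support this: difficult cases in which TGA was attempted for PVI are retained, and the direction of any time difference is unknown. Nor do they support reading the 10% attrition as five subjects with 0% TGA.

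**Conclusion.** The inconsistency is real. Under the SAP as written, procedural summaries omit inserted subjects with no TGA for PVI, and the TGA and Q-mode shares omit those ablated only in other modes.

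The importance is modest. Because TGA is the required first mode, few subjects should be affected. The overstatement of the TGA share runs from 0% to 11.1% in relative terms. The top of that range needs five excluded subjects, all ablated without TGA, and a share defined as a mean of per-subject percentages. One such subject gives 2.0%; subjects with no RF change nothing. Any shift in mean procedure time is at most 6.0 minutes in either direction under the assumed differences. The study tests no hypothesis, and neither primary endpoint is touched.

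**What to change.** Name the same population for procedural data in Protocol 14.8.3, Protocol 14.8.4.3 and SAP 10.4:

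- Summarise procedural data in the Safety Population, with the Effectiveness Population as a second column.
- Compute the TGA and Q-mode shares among subjects with any RF delivered, entering 0% TGA where RF was given only in other modes. State whether the share is a per-subject mean or a pooled ratio.
- Report the number of inserted subjects without TGA for PVI, with reasons.

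The cost is a few sentences and one table column. The reported TGA share may come out slightly lower. Readers who prefer the TGA-treated set lose nothing, because it is still shown.

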10.5 Plans for Interim Analysis

No interim analyses are planned for this study.

10.6 Handling of Missing Data

Missing questions will be queried for reasons and handled on an individual basis. No missing data imputation will be performed.

10.7 Subgroup Analyses

For the primary and secondary endpoints, subgroup analysis will be performed for the following subgroups. Effectiveness population will be used to primary and secondary effectiveness endpoints and safety population will be used for primary and secondary safety endpoint.

- TGA application mode used only for PVI vs. the application with combination TGA and Q-mode for PVI in the Effectiveness Population

- TGA application mode used only for the overall procedure vs. the application with combination TGA and Q-mode for the overall procedure in the Safety Population

Appendix: Tables, Listings and Graphs Shells

The tables, listings and graphs shells will be approved and provided separately.

End of Document
